## **6.9 Schedule of study assessments**

Assessment	Screening	Day 1 – 7	6 – 12 months post PET-CT scan
Assessment of Eligibility Criteria			
Written informed consent			
Demographic data, contact details			
Blood samples as per standard clinical care and study protocol			
12-lead ECG as per standard clinical care			
Coronary angiogram as per standard clinical care			
Transthoracic Echocardiogram as per standard clinical care			
Urinary pregnancy test			
18F-GP1 injection and waiting period			
PET-CT scan of heart			
CT Coronary angiogram			
Review of clinical notes looking for recurrent myocardial infarction, stroke or transient ischaemic attack, pulmonary embolism, all haemorrhage, current medications and death			
A standardized study questionnaire will be posted or sent via email			

## 6.10 LONG TERM FOLLOW UP ASSESSMENTS

We will then follow participants up following their PET-CT scan. This will be performed once between 6 and 12 months following their myocardial infarction, with subsequent follow up used to obtain as much data as possible. We will collect data on recurrent myocardial infarction, stroke or transient issue attack (TIA), pulmonary embolism, all haemorrhage, current medications and death. A standardized questionnaire will be posted or sent via email to the participants and a review of electronic medical notes will be undertaken between 6 and 12 months to collect this data. A telephone call to patients will be considered if patients do not return the questionnaire or further clarification is needed. Prior to contacting participants, we will check case notes to ensure the participants are not deceased and contact would distress relatives.

## 6.11 STORAGE AND ANALYSIS OF SAMPLES

Blood samples for storage will be frozen and kept for a minimum of five years. It will be stored in a locked freezer in appropriately secured premises in the Laboratory at Edinburgh Royal Infirmary. The retained blood samples and participants data (including CT/PET and MRI images) will be used for secondary studies separate to this study as hypothesis arise. Anonymised blood samples may be sent to other academic institutions or commercial companies for analysis.

## 7 DATA COLLECTION

### *Clinical Assessment*

Any changes in medication, any hospital admission or any clinical symptoms will be assessed at the study visit by the investigator.

### *Blood Sampling*

Blood samples will be collected as per standard clinical care. The results will be uploaded onto the patients electronic NSH Lothian medical record.

### *Electrocardiogram*

Electrocardiograms will be collected as per standard clinical care and uploaded onto the patient's electronic NHS Lothian medical record.

### *Echocardiography*

Echocardiography will be performed according to standard clinical care. Echocardiograms will be uploaded to the EchoPAC data storage system as part of the patient's electronic NHS Lothian medical record.

### *Computed Tomography Positron Emission Tomography*

Imaging datasets will be stored on the servers at the Edinburgh Imaging Facility for subsequent analysis. Summary imaging DICOM files will be uploaded to the PACS system as part of the patient's electronic NHS Lothian medical record.

### 7.1 Source Data Documentation

The study database will be used to document all data collection in a NHSL computer. All patient-related data will be recorded in an anonymized way. Each patient will be unequivocally identified by a trial subject number, attributed at recruitment into the study. Key data from blood results, echocardiography, CT, MRI and PET-CT/PET-MR reports will be documented in the case record form of the study database. The original reports and images will be retained by the imaging core laboratory for future reference.

## 8 DATA MANAGEMENT

Patient NHS electronic records will be accessed following formal and explicit patient consent. Anonymised data will be made available for other researchers to use where appropriate.

All identifiable participant information (Name, age, sex, address and postcode, CHI number, telephone number, email address, height, weight, clinical condition, date of study enrolment and date of PET-CT scan.) will be stored in a secure manner accessible only to members of the research team. CHI number is required to review participants relevant medical history, medications, medical imaging and standard of care intervention results. This will be stored on an NHS password protected onedrive excel file.

All computers will be encrypted and password protected. Electronic data will be stored on (2-step) password-protected computers (University laptop and NHS computers) and only accessible to the study investigators. No personal identifiable information including CHI numbers will be accessed by members outside the research team or NHS Lothian.

All University of Edinburgh employed researchers and study staff will complete the Data Protection Training through Learn.

All University of Edinburgh employed researchers, students and study staff will complete the Information Security Essentials modules through Learn and will have read the minimum and required reading setting out ground rules to be complied with.

Only study subject number will be transferred to the password protected University laptop.

The study will be guided by the principles of Good Clinical Practice and Data Protection Act in ensuring the confidentiality of personal data. Participant consent forms will contain personal data and a linked participant identification number. Hard copies of consent forms will be stored in a secure filing cabinet in a locked University Office ([name]). Study data will be kept on University password protected computers as linked anonymised data. This will enable the identification of each participant's data during the study, in order for any participant to withdraw and have personal data destroyed if they wish. All data will be anonymised after the study period.

### **8.1 Personal Data**

The following personal data will be collected as part of the research:

- Name, age, sex, address and postcode, CHI number, height, weight, clinical condition, date of study enrolment and date of PET-CT scan
- Personal data will be stored or accessed for a period of 6 to 12 months after the study has ended on a NHSL password protected onedrive excel file to allow participants to be identified so we can follow up on their management and clinical course. Thereafter, anonymised data may be stored for a period of up to five years. No personal identifiable data will be transferred to the University of Edinburgh.

### **8.2 Data Information Flow**

All data collected or generated by the study (including personal data) will not be transferred to any external individuals or organisations outside of the Sponsoring organisation(s).

### **8.3 External Transfer of Data**

All data collected or generated by the study (including personal data) will not be transferred to any external individuals or organisations outside of the Sponsoring organisation(s).

### **8.4 Data Controller**

The data controller is the University for Edinburgh and NHS Lothian. The data controller is the organisation who determines the purposes for which, and the manner in which, any personal data are processed.

### **8.5 Data Breaches**

Any data breaches will be reported to the University of Edinburgh ([[contact]](mailto:[contact])) and NHS Lothian ([[contact]](mailto:[contact])) Data Protection Officers who will onward report to the relevant authority according to the appropriate timelines if required.

## 9 STATISTICS AND DATA ANALYSIS

### 9.1 SAMPLE SIZE CALCULATION

We have found that  $^{18}\text{F}$ -GP1 is markedly discriminatory for the presence of thrombus with an accuracy of 96% with 100% specificity and false negatives predominantly seen in patients imaged beyond 7 days from presentation (37). The prevalence of coronary thrombosis in patients with myocardial infarction and non-obstructive coronary arteries is unknown but estimates suggest that plaque disruption may be as high as one third of cases although it is unclear if this is bystander disease or the cause of the infarction (19). We have estimated that routine clinical evaluation may suggest thrombus in 10-20% of patients with myocardial infarction and non-obstructive coronary arteries. For 80-90% power at two-sided  $p < 0.05$ , we will require a study population of 36-50 to detect an incidence of thrombosis of 25-40%. Population sizes for coronary thromboembolism and spontaneous coronary dissection are based on the proof-of-principle of the detection of coronary thrombosis and have greater than 95% power to detect a prevalence of coronary thrombus in over two thirds of patients.

### 9.2 PROPOSED ANALYSES

As with our previous studies, image analysis will be performed on bespoke PET analysis software from our long-standing collaborators (FusionQuant, Cedars Sinai Hospital, Los Angeles) that provides automated motion correction and advanced cardiovascular PET quantification (31, 32, 38). After accurate co-registration of the PET and CT data sets,  $^{18}\text{F}$ -GP1 uptake will be quantified within regions of interest around areas of thrombus on the CT images.

Descriptive statistics will incorporate numbers and proportions, means and standard deviations or median and interquartile ranges. Proportions will be compared with Chi-squared test and continuous variables will be compared with regression analysis, Student's *t*-test or analysis of variance with repeated measures for longitudinal assessments. Statistical significance will be taken as two-sided  $p < 0.05$ .

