#### **1.1.2 Universal definition of myocardial infarction**

Acute myocardial infarction is defined as cardiomyocyte injury and necrosis in a clinical setting consistent with acute myocardial ischaemia. The fourth universal definition of myocardial infarction describes five subtypes of acute infarction (2). Type 1 myocardial infarction is characterised by underlying atherosclerotic plaque disruption (rupture, ulceration, fissuring, erosion, or calcific nodules) resulting in intraluminal thrombosis, distal coronary embolisation and intraplaque haemorrhage that ultimately cause myocyte necrosis (3, 4). In contrast, type 2 myocardial infarction is classified as an ischaemic myocardial injury secondary to oxygen supply and demand mismatch, and importantly is not a consequence of atherosclerotic plaque rupture and coronary atherothrombosis. However, some causes of type 2 myocardial infarction do involve intracoronary thrombus including coronary thromboembolism and spontaneous coronary artery dissection. Currently, invasive coronary angiography remains the primary modality to identify patients presenting with plaque related disruption and coronary thrombosis, ultimately providing the distinction between type 1 and type 2 myocardial infarction. However, it is not always definitive (5) and only 10-20% of patients presenting with type 2 myocardial infarction undergo further investigations to identify the presence of underlying coronary artery disease or to exclude coronary atherothrombosis (6). Indeed, we recently demonstrated comprehensive cardiac imaging and coronary angiography that identified two thirds of patients had previously unrecognised underlying coronary artery disease, and this resulted in diagnostic reclassification of many patients (7). These standard techniques were however unable to determine whether this plaque was implicated in the presentation or simply a bystander finding. A non-invasive imaging technique to reliably detect intracoronary thrombus and facilitate this distinction would therefore be of major clinical value.

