## **4 STUDY POPULATION**

### **4.1 NUMBER OF PARTICIPANTS**

We will recruit two patient populations after invasive coronary angiography has been completed. We have established comparator control populations including 50 patients with stable coronary artery disease (no angina or recent myocardial infarction) and valvular heart disease who underwent F-GP1 cardiac PET-CT as part of a concurrent study (NCT04073875) (34).

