## **6.7 Hybrid $^{18}\text{F}$ -GP1 positron emission tomography and coronary computed tomography coronary angiography**

$^{18}\text{F}$ -GP1 will be synthesized by our radiochemistry facility, the Edinburgh Imaging Facility Radiochemistry (EIFR), which is co-located within our Edinburgh Imaging Facility, Queens Medical Research Institute (EIF QMRI) using our well-established protocols. Each patient will undergo  $^{18}\text{F}$ -GP1 PET/CT coronary angiography imaging on our hybrid scanner (Biograph mCT, Siemens) as soon as practical after their index event and within a maximum of 7 days from symptom onset. In our previous studies the  $^{18}\text{F}$ -GP1 signal diminished after this time point (35). Patients will initially be injected with 250 MBq  $^{18}\text{F}$ -GP1, before resting in a quiet environment for 60 min. A low-dose attenuation correction CT scan (120 kV, 50 mAs, 5/3 mm) will be followed by acquisition of PET data in list mode using a two 20-min bed position centred on the thoracic aorta and heart. A contrast-enhanced CT coronary angiogram will then be performed. After optimal co-registration of the CT and PET data, regions of interest will be drawn for PET quantification around areas of uptake in the coronary arteries, ascending and arch of the aorta as well as the atria and ventricles of the heart. Mean and maximum standardised uptake values (SUV) for  $^{18}\text{F}$ -GP1 uptake will be measured. Tissue to background ratio (TBR) will also be calculated after correcting thrombus uptake for tracer activity in the blood pool of the right atrium as described previously (37).

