## **6.8 Myocardial infarction classification**

Following the completion of all standard of care investigations the participants investigations will be presented to a panel of cardiology experts from the cardiology consultant body at the Royal Infirmary of Edinburgh who will be asked to classify the myocardial subtype using the Universal definition of myocardial infarction (2). This will help to ensure, with addition of the usual care team myocardial infarction classification, a robust classification of the myocardial infarction subtype for each patient.

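### Is the chi-squared test in Protocol 9.2 the wrong test for the cohort 1 comparison that 9.1 sizes at 36-50 patients?

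*Protocol*

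**What the plan says.** Section 9.2 is a short list of methods. For proportions it gives one sentence, "Proportions will be compared with Chi-squared test", without saying which proportions or against what. For continuous variables it names regression, the t-test and repeated-measures analysis of variance.

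Section 9.1 carries the sample size. For 80-90% power at a two-sided 5% level, "we will require a study population of 36-50 to detect an incidence of thrombosis of 25-40" per cent. The only rate placed beside this is that "routine clinical evaluation may suggest thrombus in 10-20% of patients" with this type of infarction. Section 9.1 does not say whether that rate is a fixed reference, a second assessment of the same patients or a separate group. For the small cohorts it says that their sizes "have greater than 95% power to detect a prevalence of coronary thrombus in over two thirds of patients".

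Section 3 calls the study a case-control cohort study, and section 4.1 names the controls: "We have established comparator control populations including 50 patients with stable coronary artery disease" and valvular heart disease, scanned in a concurrent study. The primary endpoint (2.2.1) is the tracer's target-to-background ratio, a continuous measure. Presence of platelet activation is a secondary endpoint (2.2.2), although frequency appears in the primary objective (2.1.1).

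**The concern.** A reader who takes chi-squared in its usual sense, a comparison of two independent groups, finds that it does not lead to 36-50. The figure comes out of a one-sample calculation instead. It would then seem that the study is sized for one test and analysed with another.

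Two consequences would matter:

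- A one-sample test needs a single reference rate, and 9.1 offers a range. If the rate were picked after the scans were read, the choice could decide significance.
- If the scan were meant to be compared with routine evaluation in the same 50 patients, the data would be paired. An independent-groups chi-squared would then ignore the pairing and lose power.

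A smaller worry is that groups of 10 set against 50 controls give expected counts below 5.

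**Working it through.** **Inputs.** Two-sided alpha 0.05, power 80-90%, target incidence 25-40%, routine-evaluation rate 10-20%, stated size 36-50 (all from 9.1); cohort 1 of 50 (4.1.1); 50 controls (4.1). No dropout is stated, and none is applied.

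**Step 1. Reproduce the plan's figure.** One-sample normal approximation:

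n = [1.960·√(p0(1−p0)) + z·√(p1(1−p1))]² / (p1−p0)², with z = 0.842 for 80% power and 1.282 for 90%.

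For p0 = 0.20 and p1 = 0.40:

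- 80%: (1.960×0.400 + 0.842×0.490)² / 0.04 = 35.8, rounded up to 36
- 90%: (1.960×0.400 + 1.282×0.490)² / 0.04 = 49.8, rounded up to 50

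This matches 36-50, but it is not the only fit. One third against 15% gives 35.8 and 50.6. A paired (McNemar) calculation for 40% against 20%, with no patient positive on routine evaluation and negative on the scan, gives 37 and 49. The fixed 20% is therefore an inference.

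**Step 2. Independent groups.** For 20% against 40% the usual two-proportion formula gives 81.2 and 108.2, so 82 and 109 per group; 50 against 50 has 59% power. Within the stated ranges the only independent-groups reading that comes near is 40% against 10% with continuity correction (38 and 49 per group).

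**Step 3. Does the choice of test change a one-sample decision?** The one-sample chi-squared statistic is n(p̂−p0)²/[p0(1−p0)], with critical value 3.84. The exact p-value is the two-sided minimum-likelihood version.

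| Positives of 50 | Reference | Chi-squared | Exact p |
|---|---|---|---|
| 15 | 20% | 3.13 | 0.109 |
| 16 | 20% | 4.50 | 0.049 |
| 9 | 10% | 3.56 | 0.092 |
| 10 | 10% | 5.56 | 0.030 |

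Both tests reject from 16 against 20% and from 10 against 10%. Replacing chi-squared with this exact test changes no decision. The doubled-tail exact p-value is stricter: 0.062 at 16, so rejection starts at 17, and power at 40% against 20% falls from 90% to 84%.

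**Step 4. How much depends on the reference rate?** Results of 10-15 positives pass against 10% and fail against 20%.

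| True rate | P(10-15 of 50) | Power against 20% |
|---|---|---|
| 25% | 67% | 17% |
| one third | 36% | 63% |
| 40% | 9% | 90% |

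Against 10%, power at a true 25% is 84%. The dependence is real, but it comes from the range in 9.1 and would be the same with any one-sample test.

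**Step 5. Cohort 1 against controls.** At 25% against 0%, the expected number of positives per group is (12.5 + 0)/2 = 6.25, above 5. At 25% against an assumed 2%, chi-squared with 50 per group has 97% power. The 2% is an assumption; the protocol gives no control rate.

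**Step 6. Paired reading.** Section 6.7 says "Each patient will undergo" the scan, and section 6.8 describes an expert panel "who will be asked to classify the myocardial subtype using the Universal definition of myocardial infarction". The panel's product is a subtype. Section 1.1.2 notes that "some causes of type 2 myocardial infarction do involve intracoronary thrombus including coronary thromboembolism and spontaneous coronary artery dissection", so subtype cannot stand for thrombus yes or no. No section sets the panel reading against the scan. A paired test would serve a comparison that the protocol does not plan.

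**Step 7. Groups of 10 against 50.** At two thirds against an assumed 10%, power is 97% with uncorrected chi-squared and 96% with Fisher's test. At 30% against 2% it is 83% and 68%. At common rates of 2-5% the uncorrected test has a type I error of 5.6-7.3%, and Fisher's 0.6-1.2%. One errs slightly high and the other low.

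**The case for a change.** The strongest contrary case is that both the test and the sample size stand in the protocol, and that in the ordinary sense of chi-squared they do not agree. On that view the mismatch cannot be put down to detail left for later. The controls appear in neither 9.1 nor 9.2, so it is not clear that chi-squared was meant for them. At 25%, the lower end of the targets in 9.1, two studies in three would fall where an unstated reference decides significance. If the comparison were paired, independent chi-squared would have 60-64% power at 20% against 40%, and 53% at 10% against 25%, below the planned 80-90%. Mid-p McNemar would reach 98% and 89% if every routine positive were also scan-positive.

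Part of this stands: 9.1 names neither the test, the comparator nor the single rate behind 36-50. The rest does not carry. Chi-squared has a one-sample form, and that form is the calculation that reproduces 36-50, so the sections can be read together. The dependence on the reference belongs to 9.1 and is no fault of the test. The paired case rests on a comparison that no section states and on an overlap the protocol does not give. If scan and routine findings were unrelated, McNemar would have 57% and 49% power, no better than chi-squared.

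**Conclusion.** The concern does not call for a change. The sentence in 9.2 is a general statement of method, and nothing shows it to be wrong. It suits cohort 1 against the 50 controls, and its one-sample form fits the sample size.

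The alternatives bring no clear gain. The exact binomial test has the same cut-offs at n=50, or costs six points of power (90% to 84%) in its doubled-tail version. McNemar's test answers a comparison that is not planned. Fisher's test for the groups of 10 exchanges a small excess in type I error for lower power in some settings, and it hardly matters near the planned effect.

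What is left is a gap in description: the reference rate and test behind 36-50 are unstated. An analyst would settle these in the SAP, where a protocol commonly leaves them, and the 36-50 figure itself reproduces. The size of that gap is the 67%, 36% and 9% above. These figures assume n=50, two-sided 5% tests and 10% and 20% as the candidate references. The fixed 20% behind 36-50 is inferred, since one third against 15% fits almost as well.

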cardiovascular conditions (34, 35). We have recently undertaken studies in patients with coronary atherothrombosis in acute type 1 myocardial infarction (35). This was the first demonstration that non-invasive imaging can identify *in vivo* intracoronary thrombus in patients presenting with acute myocardial infarction, and for this work, [name] was awarded the European Society of Cardiology Young Investigator Award in 2021. We have confirmed the high selectivity and specificity of  $^{18}\text{F}$ -GP1 binding to activated platelets within fresh human thrombus and coronary thrombectomy specimens, and importantly we have observed  $^{18}\text{F}$ -GP1 uptake only occurs within the culprit coronary arteries of those with acute myocardial infarction (35). For example, in patients with triple vessel disease, coronary  $^{18}\text{F}$ -GP1 uptake was only seen at the site of the culprit lesion. We have also demonstrated preliminary findings of focal  $^{18}\text{F}$ -GP1 uptake at the site of spontaneous coronary artery dissection, coronary thromboembolism (36) and extra-coronary thrombus including unrecognized left ventricular and atrial thrombus, as well as infarct-related intramyocardial  $^{18}\text{F}$ -GP1 uptake. This changed both the diagnosis (type 1 reclassified as type 2 myocardial infarction) and the treatment (initiation of anticoagulation) of patients presenting with acute myocardial infarction. These data demonstrate the feasibility of identifying patients with intracoronary thrombus and type 1 myocardial infarction, and those with type 2 myocardial infarction caused by spontaneous coronary artery dissection and coronary thromboembolism. Importantly the pattern of  $^{18}\text{F}$ -GP1 distribution differs among these three conditions, allowing their differentiation. This technique holds major promise in aiding the classification of myocardial infarction, especially in patients with myocardial infarction and non-obstructive coronary arteries or where the presence of coronary thrombosis is unclear.

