## **3 STUDY DESIGN**

This will be a prospective observational case-control cohort study

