#### **4.1.2 Cohort 2: Patients with coronary causes of type 2 myocardial infarction**

We will recruit 10 patients with coronary artery thromboembolism and 10 patients with spontaneous coronary artery dissection. Finally, we will include 10 subjects who have had iatrogenic coronary artery dissection or intramural haematoma as a complication of their percutaneous coronary intervention.

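### Section 9.2 fixes chi-squared for all proportions with no small-count alternative, which is unreliable for a Cohort 2 group of 10 against the 50 controls (minor)

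*Protocol*

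**What the plan says.** Protocol section 9.2 gives one rule for binary outcomes: "Proportions will be compared with Chi-squared test". It adds "Statistical significance will be taken as two-sided" p<0.05. It does not mention a continuity correction, an exact test or a rule for sparse tables.

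The group sizes are in section 4.1.2: "We will recruit 10 patients with coronary artery thromboembolism and 10 patients with spontaneous coronary artery dissection", and then "we will include 10 subjects who have had iatrogenic coronary artery dissection or intramural haematoma". Section 4.1 supplies the comparator: "We have established comparator control populations including 50 patients with stable coronary artery disease". Section 3 describes the design: "This will be a prospective observational case-control cohort study".

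Two statements bear on how many controls will be positive. Section 9.1 reports "an accuracy of 96% with 100% specificity" for the tracer, and section 1.1.5 says that "uptake only occurs within the culprit coronary arteries of those with acute myocardial infarction". Section 9.1 sizes the thromboembolism and spontaneous dissection groups as proof of principle, with more than 95% power if over two thirds are positive. It gives no expected prevalence for the iatrogenic group. Presence of platelet activation is a secondary endpoint (section 2.2.2); the primary endpoint is based on a target to background ratio (section 2.2.1).

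**The concern.** Pearson's chi-squared test relies on a large-sample approximation that breaks down when expected counts are small. With 10 patients on one side and almost no positives among 50 controls, the expected number of positives in the group of 10 can be well below 1. The p-value then has little to do with the true tail probability.

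Two things are at stake. First, a table with very few positive scans could be reported as significant when an exact test would not support that, and the error would favour the tracer. Second, section 9.2 leaves the correction open, so the same data and the same sentence can give opposite verdicts depending on a software setting.

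**Working it through.** **Inputs.** Cohort 2 group n=10 and controls n=50 (4.1.2, 4.1); two-sided alpha 0.05 (9.2); anticipated positivity two thirds (9.1). The protocol states no control positive rate. From 100% specificity and culprit-only uptake I assume it is low, and show 0 to 10%.

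**1. The plan's own figure.** Section 9.1 does not say which comparison its power of more than 95% refers to. For 10 v 50,

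power = Φ{ [|p1 − p0| − 1.96·√(p̄(1−p̄)(1/10 + 1/50))] / √(p1(1−p1)/10 + p0(1−p0)/50) }.

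With p1=2/3 and p0=0.10: p̄ = (6.667+5)/60 = 0.194, and (0.567 − 1.96×0.1371)/0.1550 = 1.92, so power is 97.3%. Control rates of 0, 2% and 5% give 99.9%, 99.7% and 99.3%. The stated figure is reproduced.

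**2. Single tables.** For 1/10 v 0/50:

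- Smallest expected count: 10 × 1/60 = 0.17.
- Pearson, uncorrected: 60×(1×50 − 9×0)² / (10×50×1×59) = 150000/29500 = 5.085, p=0.024.
- Yates: 60×(50 − 30)² / 29500 = 0.814, p=0.367.
- Fisher: the only positive falls in the group of 10 with probability 10/60, p=0.167.

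| Table | Smallest expected count | Pearson p | Yates p | Fisher p |
|---|---|---|---|---|
| 1/10 v 0/50 | 0.17 | 0.024 | 0.367 | 0.167 |
| 2/10 v 0/50 | 0.33 | 0.001 | 0.024 | 0.025 |
| 1/10 v 1/50 | 0.33 | 0.198 | 0.748 | 0.308 |
| 2/10 v 1/50 | 0.50 | 0.017 | 0.112 | 0.069 |
| 7/10 v 0/50 | 1.17 | <0.0001 | <0.0001 | <0.0001 |

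**3. Exact type I error.** Sum the binomial probabilities of all significant tables among the 11 × 51 possible, with the same rate in both groups. At 2%, the main terms for uncorrected Pearson are:

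- at least 1/10 with 0/50: (1 − 0.98^10) × 0.98^50 = 0.1829 × 0.3642 = 0.0666
- at least 2/10 with 1/50: 0.0162 × 0.3716 = 0.0060
- at least 3/10 with 2 or 3 of 50: 0.0009 × 0.2465 = 0.0002

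The total is 7.3%.

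| Common rate | Pearson, uncorrected | Fisher |
|---|---|---|
| 0.5% | 3.8% | 0.1% |
| 1% | 5.9% | 0.3% |
| 2% | 7.3% (about the maximum) | 0.6% |
| 3% | 7.0% | 0.9% |
| 5% | 5.6% | 1.2% |
| 10% | 4.4% | 1.6% |

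At these low rates the excess over 5% is confined to roughly 0.75% to 6%, and every significant result that contributes has the cases higher, where the nominal share is 2.5%.

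**4. Power after changing the test** (two thirds positive, exact enumeration, 10 v 50):

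| Control rate | Pearson | Fisher |
|---|---|---|
| 0 | >99.9% | 99.96% |
| 2% | 99.9% | 99.6% |
| 5% | 99.5% | 98.7% |
| 10% | 97.3% | 95.6% |

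**5. 10 v 10 comparisons.** Here uncorrected chi-squared has a maximum size of about 4.2%, so it does not exceed nominal. Fisher would cut power for two thirds v 2% from 94% to 85%.

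**The case against.** Four points can be made for leaving the text alone.

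- **The comparison is implied, not specified.** No section says that the proportion positive in a Cohort 2 group will be tested against controls; a descriptive report could meet the endpoint. This stands as a limit on the point. But a case-control design with a named comparator makes the test a natural one, and 9.2 itself chooses the method.
- **The premises pull against each other.** If specificity is truly 100%, a positive scan is a true positive and the null rate of zero gives no type I error. That is correct, and at a common rate of 0.5% the error is only 3.8%. The inflation needs specificity slightly below 100%. Even 0/50 observed positives does not rule that out: the upper 97.5% limit is 1 − 0.025^(1/50) = 7.1%, which covers the whole affected range.
- **The expected data lie far from the problem tables.** At two-thirds positivity the chance of exactly 1/10 is 10 × (2/3) × (1/3)^9 = 0.03%. The chance that Pearson and Fisher disagree at all is 0.03%, 0.25% and 0.8% for control rates of 0, 2% and 5%. This stands for the two groups with a stated expectation; the iatrogenic group has none.
- **A small-count rule can sit in the analysis plan.** It often does. But the protocol does not leave the test open: it names one.

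A reader might infer that any single positive scan in a group of 10 would be declared significant because almost all controls are negative. The documents do not support that. It takes exactly 0/50 positive controls (1/10 v 1/50 gives p=0.198) and an uncorrected test, which 9.2 does not specify.

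**Conclusion.** The point holds as a minor one, worth a cheap improvement. For a Cohort 2 group against the 50 controls, uncorrected chi-squared is unreliable at low positive rates. Its type I error reaches at most 7.3% against a nominal 5% in the affected range, an excess of 2.3 percentage points, in the direction that favours the tracer. Below about 0.75% there is no excess.

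This rests on three assumptions: that the comparison with controls is made, that no continuity correction is applied, and that the true positive rate is low but not zero. It concerns secondary proof-of-principle groups. It gives no ground to doubt the primary endpoint, the Cohort 1 sample size or the stated Cohort 2 power, and at the anticipated positivity the conclusion does not depend on the test.

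**What to change.** In section 9.2, add that comparisons of a Cohort 2 group with the controls use an exact test (Fisher's, or Boschloo's, with one named in advance) when any expected count is below 5, and that chi-squared is kept otherwise.

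With 10 v 50 and m positives in total, the expected counts in the group of 10 are 10m/60 and 10(60 − m)/60. Both reach 5 only at m=30, so in practice the rule means an exact test for these comparisons. It should not be extended to every comparison with a group of 10: between two groups of 10 chi-squared keeps its size and Fisher would lose power for no gain.

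The cost is one sentence and a small loss of power with Fisher at two-thirds positivity: 99.9% to 99.6% at a 2% control rate and 97.3% to 95.6% at 10%, still above the stated 95%. No sample size changes.
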